### **Prior/Concomitant Therapy**

14. Has received a dose of any pneumococcal vaccine prior to study entry.
15. Has received >1 dose of monovalent hepatitis B vaccine or hepatitis B based combination vaccine prior to study entry.
16. Has received a dose of rotavirus vaccine prior to study entry.
17. \*Meets one or more of the following systemic corticosteroid exclusion criteria:
  - a. Has received systemic corticosteroids (equivalent of  $\geq 2$  mg/kg total daily dose of prednisone or  $\geq 20$  mg/d for persons weighing  $>10$  kg) for  $\geq 14$  consecutive days and has not completed this course of treatment at least 30 days prior to study randomization.
  - b. Has received systemic corticosteroids within 14 days prior to the first dose of vaccine at randomization.
  - c. Is expected to require systemic corticosteroids within 30 days after each vaccination during conduct of the study.

**Note:** Topical, ophthalmic and inhaled steroids are permitted.

18. \*Has received other licensed non-live vaccines within the 14 days before receipt of first dose of study vaccine.
19. \*Has received a licensed live virus vaccine within the 30 days prior to receipt of first dose of study vaccine.

20. Has received a blood transfusion or blood products, including immunoglobulins.

### **Prior/Concurrent Clinical Study Experience**

21. Has participated in another clinical study of an investigational product before the beginning or anytime during the duration of the current clinical study. Participants enrolled in observational studies may be included; these will be reviewed on a case-by-case basis for approval by the Sponsor.

### **Other Exclusions**

22. Has any other reason that, in the opinion of the investigator, may interfere with the evaluation required by the study. Reasons may include, but are not limited to, being unable to keep appointments or planning to relocate during the study.

23. Is or has an immediate family member (eg, parent/legal guardian or sibling) who is investigational site or Sponsor staff directly involved with this study.

**For items with an asterisk (\*), if the participant meets these exclusion criteria, Visit 1 may be rescheduled for a time when these criteria are not met.**

### **5.3 Lifestyle Considerations**

No lifestyle restrictions are required.

### **5.4 Screen Failures**

Screen failures are defined as participants whose legally acceptable representative provides consent to participate in the clinical study, but are not subsequently randomized in the study. A minimal set of screen failure information is required to ensure transparent reporting of screen failure participants to meet the Consolidated Standards of Reporting Trials (CONSORT) publishing requirements and to respond to queries from regulatory authorities. Minimal information includes demography, screen failure details, eligibility criteria, and any AEs or SAEs meeting reporting requirements as outlined in the data entry guidelines.

### **5.5 Participant Replacement Strategy**

A participant who withdraws from the study will not be replaced.

## **6 STUDY INTERVENTION**

Study intervention is defined as any investigational intervention(s), marketed product(s), placebo, or medical device(s) intended to be administered to a study participant according to the study protocol.

Clinical supplies (V114, Prevnar 13™, and concomitant vaccines listed in [Table 3](#)) will be packaged to support enrollment. Clinical supplies will be affixed with a clinical label in accordance with regulatory requirements.

## 6.1 Study Intervention(s) Administered

The blinded study interventions to be used in this study are outlined in [Table 2](#). Licensed pediatric vaccines will be administered concomitantly across all intervention groups; refer to [Table 3](#) for dosing schedule and refer to product labeling for dose formulation, dose strength, dosage level, etc.

Table 2 Study Interventions

Arm Name	Arm Type	Intervention Name	Type	Dose Formulation	Unit Dose Strength(s)	Dosage Level(s)	Route of Admin	Vaccination Regimen	Use	IMP/N IMP	Sourcing
1	Active Comparator	Prevnar 13™	Biological/ Vaccine	Sterile suspension	Refer to product labeling	0.5 mL	IM	Single dose at Visits 1, 2, 3, and 5 (~2, 4, 6, and 12 to 15 months of age, respectively)	Experimental	IMP	Central
2	Experimental	Prevnar 13™	Biological/ Vaccine	Sterile suspension	Refer to product labeling	0.5 mL	IM	Single dose at Visits 1, 2, and 3 (~2, 4, and 6 months of age, respectively)	Experimental	IMP	Central
		V114	Biological/ Vaccine	Sterile suspension	Refer to IB	0.5 mL	IM	Single dose at Visit 5 (~12 to 15 months of age)	Experimental	IMP	Central
3	Experimental	Prevnar 13™	Biological/ Vaccine	Sterile suspension	Refer to product labeling	0.5 mL	IM	Single dose at Visits 1 and 2 (~2 and 4 months of age, respectively)	Experimental	IMP	Central
		V114	Biological/ Vaccine	Sterile suspension	Refer to IB	0.5 mL	IM	Single dose at Visits 3 and 5 (~6 and 12 to 15 months of age, respectively)	Experimental	IMP	Central
4	Experimental	Prevnar 13™	Biological/ Vaccine	Sterile suspension	Refer to product labeling	0.5 mL	IM	Single dose at Visit 1 (~2 months of age)	Experimental	IMP	Central
		V114	Biological/ Vaccine	Sterile suspension	Refer to IB	0.5 mL	IM	Single dose at Visits 2, 3, and 5 (~4, 6, and 12 to 15 months of age, respectively)	Experimental	IMP	Central
5	Experimental	V114	Biological/ Vaccine	Sterile suspension	Refer to IB	0.5 mL	IM	Single dose at Visits 1, 2, 3, and 5 (~2, 4, 6, and 12 to 15 months of age, respectively)	Experimental	IMP	Central

Admin = administration; IB = Investigator's Brochure; IM = intramuscular; IMP = investigational medicinal product; NIMP = non-investigational medicinal product

The definition of IMP and NIMP is based on guidance issued by the European Commission. Regional and/or country differences of the definition of IMP/NIMP may exist. In these circumstances, local legislation is followed.

All supplies indicated in [Table 2](#) will be provided per the "Sourcing" column depending upon local country operational requirements. Every attempt should be made to source these supplies from a single lot/batch number.

Refer to Section 8.1.8 for details regarding administration of the study intervention.

## **6.2 Preparation/Handling/Storage/Accountability**

### **6.2.1 Dose Preparation**

There are no specific calculations or evaluations required to be performed in order to administer the proper dose to each participant. The rationale for selection of doses to be used in this study is provided in Section 4.3.

### **6.2.2 Handling, Storage, and Accountability**

The investigator or designee must confirm appropriate temperature conditions have been maintained during transit for all study intervention received, and any discrepancies are reported and resolved before use of the study intervention.

Only participants enrolled in the study may receive study intervention, and only authorized site staff may supply or administer study intervention. All study interventions must be stored in a secure, environmentally controlled, and monitored (manual or automated) area in accordance with the labeled storage conditions with access limited to the investigator and authorized site staff.

The investigator, institution, or the head of the medical institution (where applicable) is responsible for study intervention accountability, reconciliation, and record maintenance (ie, receipt, reconciliation, and final disposition records).

For all study sites, the local country Sponsor personnel or designee will provide appropriate documentation that must be completed for drug accountability and return, or local discard and destruction if appropriate. Where local discard and destruction is appropriate, the investigator is responsible for ensuring that a local discard/destruction procedure is documented.

The study site is responsible for recording the lot number, manufacturer, and expiry date for any locally purchased product (if applicable) as per local guidelines unless otherwise instructed by the Sponsor.

The investigator shall take responsibility for and shall take all steps to maintain appropriate records and ensure appropriate supply, storage, handling, distribution, and usage of study interventions in accordance with the protocol and any applicable laws and regulations.

## 6.3 Measures to Minimize Bias: Randomization and Blinding

### 6.3.1 Intervention Assignment

Treatment allocation/randomization will occur centrally using an interactive response technology (IRT) system. There are 5 study intervention arms. Participants will be assigned randomly in a 1:1:1:1:1 ratio to the study intervention listed in [Table 2](#).

### 6.3.2 Stratification

Intervention allocation/randomization will be stratified according to the following factors:

- Hepatitis B vaccination status before enrollment (Yes, No)

Stratification by hepatitis B vaccination status before enrollment is relevant for this study because the timing of the first dose of hepatitis B vaccine may have an effect on immunogenicity evaluation of the secondary endpoint related to concomitant administration of RECOMBIVAX HB™ (see Section 4.2.1.1 for details).

### 6.3.3 Blinding

A double-blinding technique will be used. V114 and Prevnar 13™ will be prepared and/or dispensed by an unblinded pharmacist or unblinded qualified study site personnel. The participant and the investigator who is involved in the clinical evaluation of the participants will remain blinded to the group assignments.

Because V114 and Prevnar 13™ have a different appearance, a member of the study site staff will be unblinded for the purposes of receiving, maintaining, preparing, and administering these study vaccines. Procedures for handling, preparing, and administering the unblinded vaccines are located in the Investigator Trial File Binder.

In order to avoid bias, the unblinded study personnel will have no further contact with study participants for any study-related procedures/assessments after administration of study vaccines, which includes all safety follow-up procedures. Additionally, blinded site personnel will not be present in the examination room when study vaccines are administered. Contact between participants and unblinded study personnel after vaccination administration is strictly prohibited. Blinded site personnel will be responsible for all safety and immunogenicity follow-up procedures after vaccine administration.

An unblinded Clinical Research Associate will monitor vaccine accountability at the study site. All other Sponsor personnel or delegate(s) and Merck Research Laboratories employees directly involved with the conduct of this study will remain blinded to the participant-level intervention assignment.

See Section 8.1.13 for a description of the method of unblinding a participant during the study should such action be warranted.

## 6.4 Study Intervention Compliance

Interruptions from the protocol specified plan for V114 or Prevnar 13™ vaccination at Visits 1, 2, 3, and 5 and concomitant vaccinations listed in [Table 3](#) require consultation between the investigator and the Sponsor and written documentation of the collaborative decision on participant management.

## 6.5 Concomitant Therapy

Medications or vaccinations specifically prohibited in the exclusion criteria are not allowed during the ongoing study (see Section 5.2 for details). If there is a clinical indication for any medication or vaccination specifically prohibited, discontinuation from study intervention may be required. The investigator should discuss any questions regarding this with the Sponsor Clinical Director. The final decision on any supportive therapy or vaccination rests with the investigator and/or the participant's primary physician. However, the decision to continue the participant on study intervention requires the mutual agreement of the investigator, the Sponsor, and the participant's legally acceptable representative.

If a medical condition requires the use of a prohibitive steroid regimen, immunoglobulin, blood, or blood products during a subject's participation in this study, one of the individuals listed on the Sponsor Contact Information page must be notified as soon as possible. Any concurrent medication or medical treatment must be recorded on the appropriate eCRF. It is important to record the use of any analgesic or antipyretic medication that occurs on the day of vaccination on the eVRC and appropriate eCRF.

Other licensed pediatric vaccines will be administered concomitantly according to the recommended schedule ([Table 3](#)). In the US, the ACIP recommends that hepatitis B vaccine should be given at birth; however, guidelines for non-US counties may differ. For participants who received the first dose of hepatitis B vaccine before enrollment, RECOMBIVAX HB™ will be administered at ~2 and 6 months of age and not at ~4 months of age.

In addition to concomitant vaccines being provided in the study ([Table 3](#)), other non-study pediatric vaccines may be permitted according to local, regional, and/or country guidelines. If the participant is scheduled to receive any other non-study pediatric vaccine, the investigator should discuss this with the Sponsor Clinical Director as soon as possible. These vaccinations should be recorded on the appropriate eCRF.

During influenza season, it is anticipated that participants 6 months of age and older may be given an influenza vaccine. Influenza vaccine should be administered either 7 days prior to or 15 days after the administration of the study vaccine.

Concomitant vaccines (oral or injectable) should be administered on the same day as V114 or Prevnar 13™. RotaTeq™ is administered orally and should be given before V114 or Prevnar 13™ and other injectable concomitant vaccines. Precautions must be taken to prevent choking during the administration of oral vaccines. Other pediatric injectable

vaccines administered concomitantly should be given after V114 or Prevnar 13™. To avoid any confounding results, concomitant injectable vaccines should not be administered in the same limb as V114 or Prevnar 13™. Recommended injection-site locations for V114 or Prevnar 13™ and concomitant injectable vaccines are listed in [Table 4](#).

Documentation of which limb to use for the administration of study vaccines must be recorded on the appropriate eCRF. Injection-site AEs for V114 or Prevnar 13™ (and not for the concomitant vaccines) are being reported in this study; therefore, this information must also be recorded on the eVRC to inform the participant's legally acceptable representative of the appropriate limb to monitor for AEs related to the V114 or Prevnar 13™.

No other investigational compound or device may be administered at any time during this study without prior approval by the Sponsor.

Table 3 Concomitant Vaccine Schedule

Vaccine Tradename a (Generic Name)	Indication	Visit 1 (~2 months of age)	Visit 2 (~4 months of age)	Visit 3 (~6 months of age)	Visit 5 (~12 to 15 months of age)
RotaTeq™ b (Rotavirus Vaccine, Live, Oral, Pentavalent)	Prevention of rotavirus gastroenteritis	X	X	X	
Pentacel™ (Diphtheria and Tetanus Toxoids and Acellular Pertussis Adsorbed, Inactivated Poliovirus and Haemophilus b Conjugate (Tetanus Toxoid Conjugate) Vaccine	Prevention of diphtheria, tetanus, pertussis, poliomyelitis, and invasive disease due to Haemophilus influenzae type b	X	X	X	
RECOMBIVAX HB™ (Hepatitis B Vaccine [Recombinant])	Prevention of hepatitis B virus infection	X	X c	X	
HIBERIX™ (Haemophilus b Conjugate Vaccine [Tetanus Toxoid Conjugate])	Prevention of invasive disease caused by Haemophilus influenzae type b				X
M-M-R™ II (Measles, Mumps, and Rubella Virus Vaccine Live)	Simultaneous vaccination against measles, mumps, and rubella				X
VARIVAX™ (Varicella Virus Vaccine Live)	Prevention of varicella				X

a Tradenames for concomitant vaccines may vary depending on where clinical supplies are sourced by the Sponsor.

b RotaTeq™ is administered orally and should be given before V114 or Prevnar 13™ and other injectable concomitant vaccines.

c For participants who received the first dose of hepatitis B vaccine before enrollment, RECOMBIVAX HB™ will be provided and administered concomitantly with V114 or Prevnar 13™.

Table 4 Recommended Injection-Site Location for Study Interventions

Vaccine	Recommended Injection Site
V114 or Prevnar 13™	Right thigh
Pentacel™	Left upper thigh
RECOMBIVAX HB™	Left lower thigh
M-M-R™ II	Deltoid right arm
VARIVAX™	Deltoid left arm
HIBERIX™	Left thigh

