## 1.2 Schema

The key components of the study design are depicted in **Figure 1**.

AE = adverse event; eVRC = electronic Vaccination Report Card; INCL/EXCL = Inclusion/Exclusion Criteria; PCV13 = Prevnar 13™; PD = postdose; SAE = serious adverse event

a Randomization will be stratified by previous hepatitis B vaccination status.

b Tradenames for the concomitant vaccines may vary depending on where clinical supplies are sourced by the Sponsor.

c RotaTeq™ is administered orally and should be given before V114 or Prevnar 13™ and other injectable concomitant vaccines.

d For participants who received the first dose of hepatitis B vaccine before enrollment, RECOMBIVAX HB™ will be administered at ~2 and 6 months of age and not at ~4 months of age.

Figure 1 V114-027 Study Design

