## 4.2.1 Rationale for Endpoints

### 4.2.1.1 Immunogenicity Endpoints

Previous studies have evaluated the interchangeability of PCVs [Truck, J., et al 2016] [Ciapponi, A., et al 2016]. These studies evaluated the immune responses and reactogenicity in infants primed with Prevnar 13™ and boosted with Synflorix™ (as compared with a Prevnar 13™ booster) and in infants primed with Prevnar™ and boosted with Prevnar 13™. The primary immunogenicity endpoint of these interchangeability studies were assessed 1 month after the administration of the last scheduled dose of the PCVs.

This study will evaluate the safety, tolerability, and immunogenicity of the interchangeability between V114 and Prevnar 13™ in participants administered mixed dosing schedules of Prevnar 13™ and V114 (Groups 2, 3, and 4) compared with participants administered a complete dosing schedule of Prevnar 13™ (Group 1).

Sera from participants will be used to measure vaccine-induced anti-PnPs serotype-specific IgG for the 13 shared serotypes (1, 3, 4, 5, 6A, 6B, 7F, 9V, 14, 18C, 19A, 19F, and 23F) contained in V114 and Prevnar 13™ at 30 days after Dose 4. The primary interchangeability immunogenicity endpoint will be assessed after completion of the full PCV regimen. Anti-PnPs serotype-specific IgG responses will also be measured at 30 days following completion of the primary infant series and prior to Dose 4 to evaluate the anamnestic antibody responses and the persistence of protective immunity.

Sera from participants will also be used to measure anti HBsAg concentration using the hepatitis B enhanced chemiluminescence (ECi) assay. An anti-HBsAg concentration of  $\geq 10$  mIU/mL measured 1 to 3 months after administration of the last dose of the primary 3-dose vaccination series is considered a reliable marker of protection against hepatitis B infection [Van Damme, P. 2016]. In this study, infants will receive a total of 3 hepatitis B vaccinations (2, 4 and 6 months). For those participants who received the first dose of hepatitis B vaccine prior to enrollment in the study, hepatitis B vaccine will be administered at 2 and 6 months of age and not at 4 months. Because antibody responses and GMTs may be slightly higher when hepatitis B vaccination is initiated after 1 month of life [Schillie, S. F. 2013], randomization in this study will be stratified by previous hepatitis B vaccination status before enrollment.

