## 8 STUDY ASSESSMENTS AND PROCEDURES

- Study procedures and their timing are summarized in the SoA.
- Adherence to the study design requirements, including those specified in the SoA, is essential and required for study conduct.
- The investigator is responsible for ensuring that procedures are conducted by appropriately qualified or trained staff. Delegation of study site personnel responsibilities will be documented in the Investigator Trial File Binder (or equivalent).

- All study-related medical decisions must be made by an investigator who is a qualified physician.
- All screening evaluations must be completed and reviewed to confirm that potential participants meet all eligibility criteria. The investigator will maintain a screening log to record details of all participants screened and to confirm eligibility or record reasons for screening failure, as applicable.
- Procedures conducted as part of the participant's routine clinical management (eg, blood count) and obtained before signing of ICF may be utilized for screening or baseline purposes provided the procedure met the protocol-specified criteria and were performed within the time frame defined in the SoA.
- Additional evaluations/testing may be deemed necessary by the investigator and or the Sponsor for reasons related to participant safety. In some cases, such evaluation/testing may be potentially sensitive in nature (eg, HIV, Hepatitis C), and thus local regulations may require that additional informed consent, be obtained from the participant's legally acceptable representative. In these cases, such evaluations/testing will be performed in accordance with those regulations.

Approximately 5 mL of blood will be drawn at each of Visits 4, 5, and 6 for immunogenicity assays. The maximum amount of blood collected from each participant over the duration of the study will not exceed 15 mL.

Repeat or unscheduled samples may be taken for safety reasons or for technical issues with the samples.

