## 9.5 Analysis Populations

### 9.5.1 Immunogenicity Analysis Populations

The PP population will serve as the primary population for the analysis of immunogenicity data in this study. The PP population consists of all randomized participants without deviations from the protocol that may substantially affect the results of the immunogenicity endpoint(s). Potential deviations that may result in the exclusion of a participant from the PP population for all immunogenicity analyses include:

- Failure to receive primary infant series vaccination (V114/Prevnar 13™ Doses 1, 2, and 3) as per randomization schedule
- Receipt of prohibited medication or prohibited vaccine prior to study vaccination

Additional potential deviations that may result in the exclusion of a participant from the PP population for specific immunogenicity analyses (depending on the timepoint for analysis) include:

- Failure to receive V114, Prevnar 13™, RECOMBIVAX HB™, or RotaTeq™ according to vaccination schedule required at the timepoint for the analysis
- Failure to receive the scheduled doses of V114 or Prevnar 13™ (at least 28 days between Doses 1 and 2 and between Doses 2 and 3 [for PD3 and pre-dose 4 analysis], 12 months to 1 day prior to 16 months of age for Dose 4 [for PD4 PP analyses])
- Receipt of prohibited medication or prohibited vaccine prior to a blood sample collection
- Collection of blood sample at the timepoint for the analysis outside of the pre-specified window (as described in Section 1.3)

The final determination on protocol deviations, and thereby the composition of the PP population, will be made prior to the final unblinding of the database. Participants will be

included in the vaccination group to which they are randomized for the analysis of immunogenicity data using the PP population.

A supportive analysis using the Full Analysis Set (FAS) population will also be performed for the primary immunogenicity endpoints. The FAS population consists of all randomized participants who received all study vaccinations required at the timepoint for the analysis and have serology result. Participants will be included in the vaccination group to which they are randomized for the analysis of immunogenicity data using the FAS population.

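### Table 3 footnote c, by where its marker sits, has previously vaccinated infants given RECOMBIVAX HB at 4 months, the visit at which four other places withhold it

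*Combined protocol and SAP*

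**What the plan says.** Table 3 (Section 6.5) schedules RECOMBIVAX HB at Visits 1, 2 and 3, about 2, 4 and 6 months of age. The cells for Visits 1 and 3 carry a plain mark. Only the Visit 2 cell carries footnote c, which reads: "For participants who received the first dose of hepatitis B vaccine before enrollment, RECOMBIVAX HB™ will be provided and administered concomitantly" with V114 or Prevnar 13.

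Four other places give the rule for infants who had a hepatitis B dose before enrolment:

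- Section 1.2, Figure 1 footnote d: "RECOMBIVAX HB™ will be administered at ~2 and 6 months of age and not at ~4 months of age".
- Section 1.3, the asterisk on the Visit 2 entry of the Schedule of Activities: the same rule in the same words.
- Section 4.2.1.1: "hepatitis B vaccine will be administered at 2 and 6 months of age and not at 4 months".
- Section 6.5, in the paragraph that directs the reader to Table 3: the same rule as Figure 1 footnote d.

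Section 4.2.1.1 also fixes the intended number of doses: "infants will receive a total of 3 hepatitis B vaccinations (2, 4 and 6 months"). Exclusion criterion 15 in Section 5.2 limits prior exposure by excluding an infant who "Has received >1 dose of monovalent hepatitis B vaccine or hepatitis B based combination vaccine prior to study entry".

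**The concern.** Table 3 is a working dosing table. Sections 2.2.3, 4.1, 6.1 and 6.5 send readers to it for the concomitant vaccine schedule. Section 6.4 uses it as the list of vaccinations whose interruption would "require consultation between the investigator and the Sponsor and written documentation of the collaborative decision on participant management". A site that correctly withholds the 4-month dose could therefore look as though it were interrupting the Table 3 plan.

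The first thing at stake is an unplanned injection in a healthy infant. The second is the regimen behind H1, which measures anti-HBsAg response 30 days after Dose 3. Section 9.5.1 lists, among the deviations that may lead to exclusion from a specific per-protocol analysis, failure to receive V114, Prevnar 13, "RECOMBIVAX HB™, or RotaTeq™ according to vaccination schedule required at the timepoint for the analysis". An infant given an extra hepatitis B dose has departed from the intended schedule, and per-protocol status for H1 would need a decision.

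**Working it through.** **Reading the footnote in place.** Footnote c names no visit, so its meaning depends on the cell that carries it. Two readings are possible.

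1. Read at its marker (Visit 2, ~4 months): infants with a prior dose receive RECOMBIVAX HB at that visit. This contradicts all four places listed above.
2. Read as a general remark that these infants receive study-supplied RECOMBIVAX HB alongside the pneumococcal vaccine: true for Visits 1 and 3, but the marker on Visit 2 then has no function, and Table 3 contains no instruction to withhold the 4-month dose.

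Under either reading, the 4-month exception is missing from Table 3.

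**Dose count.** Total doses = doses before entry + doses in the study.

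- Prior doses: criterion 15 excludes more than 1, so every infant in the prior-vaccination stratum enters with exactly 1.
- Planned total: 3 (Section 4.2.1.1).

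| Infant | Schedule followed | Before entry | In study | Total |
|---|---|---|---|---|
| No prior dose | All places agree | 0 | 3 (Visits 1, 2, 3) | 3 |
| Prior dose | Figure 1, Schedule of Activities, 4.2.1.1, 6.5 text | 1 | 2 (Visits 1, 3) | 3 |
| Prior dose | Table 3 as footnoted | 1 | 3 (Visits 1, 2, 3) | 4 |

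The first two rows reproduce the planned total of 3. Table 3 as footnoted gives 4 − 3 = 1 dose too many.

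**Check on the H1 power statement.** The inputs from Section 9.9.1 are 80% evaluability, 95% response assumed in both arms, margin −0.10 and one-sided α = 0.025.

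- Evaluable: 0.80 × 180 = 144 in Group 5, and 0.80 × 360 = 288 in Groups 1 + 2.
- Standard error at the assumed rates: √[0.95 × 0.05 × (1/144 + 1/288)] = 0.0222.
- Farrington-Manning: the maximum-likelihood rates restricted to a difference of −0.10 are 0.863 and 0.963, so the null standard error is √[0.863 × 0.137/144 + 0.963 × 0.037/288] = 0.0307.
- Power = Φ[(0.10 − 1.96 × 0.0307)/0.0222] = Φ(1.79) = 96.3%.

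This agrees with the stated ~96%. (The simpler unpooled formula gives Φ(0.10/0.0222 − 1.96) = 99.4%; the plan's figure matches the restricted-variance method.) None of these inputs depends on footnote c, so the power statement stands.

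**The case against.** The strongest reply is that the intended rule is not in doubt. It is stated four times. One of those statements is in the very paragraph of Section 6.5 that leads to Table 3, and another is in the Schedule of Activities, of which Section 8 says "Adherence to the study design requirements, including those specified in the SoA, is essential and required for study conduct". Sites must also review and document receipt of a birth dose (Sections 1.3 and 8.1.5.1), so they will know which infants are affected. Taken by itself, the footnote sentence is even true of Visits 1 and 3. A site would have to overlook several correct statements to give the extra dose.

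That stands, and it is why this is an error in a footnote and not in the design. It does not rescue the footnote. The marker is on Visit 2 alone, and a dosing table should not depend on readers overriding it.

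It is also fair to say that the per-protocol consequence is uncertain. Section 9.5.1 speaks of failure to receive vaccines according to schedule, and an infant given one dose too many does not plainly meet that description. The listed deviations are potential grounds only. The documents state no clinical harm from a fourth dose, and none is asserted here.

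**Conclusion.** The footnote is wrong as written and should be corrected. The size is one unplanned hepatitis B dose (4 instead of 3) for each infant with a prior dose who is managed from Table 3 alone. The number of such infants cannot be derived, because the documents give neither the size of the prior-vaccination stratum nor how many sites would rely on that table.

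The conclusion rests on reading footnote c at the cell that carries its marker. Even without that reading, Table 3 lacks the exception.

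No between-group bias is claimed: the footnote applies equally to all five groups, and both the randomization and the H1 analysis are stratified by prior hepatitis B vaccination. The primary objectives and the H1 power are unaffected.

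**What to change.** Replace Table 3 footnote c with the wording of Figure 1 footnote d, so that infants who had a hepatitis B dose before enrolment receive RECOMBIVAX HB at about 2 and 6 months and not at about 4 months. Keep the marker on the Visit 2 cell, and notify sites.

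The cost is a one-line change by amendment or clarification letter. Sample size, randomization and analysis do not change, and Section 9.5.1 needs no edit once the footnote is right.
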